3. OBJECTIVES

3.1 Principal objective

The main objective of Predi-COVID is to identify clinical, epidemiological and omics characteristics associated with the severity of COVID-19, which will then be used to further stratify the study population into clusters of disease severity with similar patterns and disease courses.

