11.2 Sample size determination

This is a very early study which aims at understanding the severity associated with a new, poorly understood pathogen. Therefore, the sample size is not formally determined as in a clinical trial study. Recruitment of participants will depend on the emergence and spread of the virus and the resources available to the recruitment centres. The sample size should be as large as feasible and preferably without limit in order to capture as much clinical data as possible early in the outbreak. This is as well feasible because of the implementation of a national digital solution for follow up of patients.

Nevertheless, in the sub-sample study a minimum of 200 COVID-19 positive adult persons in the Predi-COVID study would allow to find a risk ratio of severe disease above 2 for the selected risk factor with a power of 80% when the prevalence of the disease is above 7% (see figure below). This number will be updated depending on new acquired knowledge (amendment to the protocol).

In the pediatric sub-sample study a minimum of 100 COVID-19 positive children in the Predi-COVID study would allow to find a risk ratio of severe disease above 3.2 for the selected risk factor with a power of 80% when the prevalence of the disease is above 7% (see figure below). This number will be updated depending on new acquired knowledge (amendment to the protocol).

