11.4 Statistical analyses

Descriptive statistics will be produced for the main endpoints, namely hospitalisation, intensive care / resuscitation admission, ventilation, their duration, death and severity of the disease. Secondary endpoints together with other variables including potential prognostic factors of the disease will also be described with mean (+- STD) or frequencies (%) as adequate.

A logistic model will be used to study whether the risks of hospitalisation, intensive care admission or intubation as well as death are associated with a specific risk factor. adjustment will be done on age, gender and other potential confounding factors.

Factors triggering the severity of the disease will be evaluated with a Mantel-Haenszel chi square to evaluate if different levels of patients' characteristics are associated with a more serious form of the disease.

Further stratification of the patient cohort will be performed through Machine learning techniques to include biological and other omics measurements. A deep phenotyping related to the symptoms of the disease as well as biosampling allowing for laboratory-based and computational analytics will be performed. The stratification approach will include data-driven tools and allow to define disease trajectories that will be translated into clinical and/or biomarker-defined subgroups

The time to conversion from the PREDI-COVID-H cohort to the PRECOVID cohort will also be studied.

[figure not shown]
Missing data will not be replaced concerning the endpoints. A replacement method such as multiple imputations through chained equations will be envisaged for the other variables and risk factors.

The limits of the study linked to the size of the sample enrolled, the extent of the effects or the selection of participants and other potential limits will be evaluated and discussed.

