ANNEX 3 :

CRF PREDI-COVID

Utilisation de la plateforme REDcap Protocole ISARIC modifié

Version française V1.0

Le CRF Predi-COVID est composé des socles CORE et DAILY du consortium ISARIC auquel des modules complémentaires ont été ajoutés. Les parties ISARIC peuvent être remplies à l'aide d'information du dossier médical ou à l'aide du patient. Les modules complémentaires sont à renseigner avec le patient.

Table des matières

[CRF ISARIC Français](#)

[SECTION PRINCIPALE](#)

[SECTION QUOTIDIENNE](#)

[Modules complémentaires](#)

[Profil](#)

[Traitements actuels \(hors traitements liés à Covid19\)](#)

CRF ISARIC Français

NOUVEAU CORONAVIRUS (nCoV) 2019

BASE DE DONNEES POUR LA CARACTERISATION CLINIQUE D'UNE INFECTION RESPIRATOIRE AIGÛE

CAHIER D'OBSERVATION PATIENT (CASE REPORT FORM – CRF)

STRUCTURATION DU CRF

Ce CRF comporte une section « PRINCIPALE » et une section « QUOTIDIENNE » pour les données clinico-biologiques.

Ce CRF est à compléter pour la section PRINCIPALE et QUOTIDIENNE lors du premier jour d'admission du patient à l'hôpital ou en service de réanimation, puis pour la section QUOTIDIENNE tous les jours jusqu'à la sortie du patient ou son décès.

Instructions générales

- Ce CRF a été créé dans le but de collecter des données obtenues lors d'un examen clinique, d'un interrogatoire, ou à partir de données médicales hospitalières inscrites dans le dossier du patient.
- Le Numéro d'Identification anonymisé du Participant se présente sous la forme d'un numéro à 3 chiffres correspondant au site, suivi d'un numéro à 4 chiffres correspondant au numéro du participant.
Vous pouvez obtenir le code qui correspond au site et vous enregistrer en contactant par e-mail le data manager du système : [contact]. Les numéros d'identification des participants devront être assignés séquentiellement pour chaque site, en commençant par le numéro 0001. Pour un centre qui recruterait des participants dans différents services hospitaliers, ou s'il est impossible d'attribuer ces numéros de manière séquentielle, il est possible d'attribuer ces numéros par bloc, ou en y ajoutant une lettre. Par exemple, le service X assignera les numéros à partir de 0001 ou A001, le service Y assignera des numéros à partir de 5001 ou B001.

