| VIH/SIDA | • O U I | • N O N | • N / A | | | | |

Hypertension

COPD

Maladie inflammatoire chronique (ex: syndrome du côlon irritable)

DEBUT DE SYMPTOMES & ADMISSION

Date du premier symptôme : [] [] [] / [] [] [] / [2] [0] [] [] []

Date d'admission dans l'établissement : [] [] [] / [] [] [] / [2] [0] [] [] []

Heure d'admission (Format 24 heures) : [] [] [] [] / [] [] [] []

Transfert depuis un autre établissement de santé ? OUI, d'un autre centre participant OUI, d'un centre non participant

- NON N/A

Si OUI : Nom de l'établissement d'origine : __ N/A

Si OUI : Date d'admission dans l'établissement d'origine (JJ/MM/AAAA) :

[] [] [] / [] [] [] / [2] [0] [] [] [A] N/A

Si OUI, il s'agit d'un autre centre participant : Numéro d'identification d'origine du patient

: Inchangé Différent : [] [] [] - [] [] [] [] N/A

Antécédent de voyage dans les 14 jours précédant la survenue des premiers symptômes ? OUI NON NC

Si OUI, localisation géographique et dates du séjour : Pays

: __ Ville ou zone géographique : __

Date de retour : [] [] [] / [] [] [] / [2] [0] [] [] [] N/A (espace supplémentaire à la fin du document si besoin) Contact avec des animaux, consommation de viande crue, piqûre d'insecte dans les 14 jours précédant la survenue des symptômes ?

- OUI NON NC N/A Si OUI, compléter la section EXPOSITION ANIMALE

SECTION PRINCIPALE

SIGNES ET SYMPTÔMES A L'ADMISSION (Données disponibles dès l'admission – dans les 24 premières heures)

Température : [] [] [] . [] °C FC : [] [] [] battements/min FR : [] [] respiration/min

PAS : [] [] [] mmHg PAD : [] [] [] mmHg Déshydratation sévère : OUI NON NC

Temps de recoloration cutanée (sternum) >2 secondes : OUI NON NC

Saturation en oxygène : [] [] [] % Sous air ambiant : OUI NON N/A ou

Oxygénothérapie : OUI NON

- N/A

SIGNES ET SYMPTÔMES A L'ADMISSION (observés/reportés à l'admission et associés à l'événement en cours)

Antécédents de fièvre

- OUI
- NON
- NC

Toux

- OUI
- NON
- NC

Expectorations associées

- OUI
- NON
- NC

Hémoptysie associée

- OUI
- NON
- NC

| | | | |
|--|-------|-------|------|
| Maux de gorge | • OUI | • NON | • NC |
| Rhinorrhée | • OUI | • NON | • NC |
| Otalgie | • OUI | • NON | • NC |
| Sifflement | • OUI | • NON | • NC |
| Douleur thoracique | • OUI | • NON | • NC |
| Myalgies | • OUI | • NON | • NC |
| Arthralgies | • OUI | • NON | • NC |
| Fatigue / Malaise | • OUI | • NON | • NC |
| Dyspnée | • OUI | • NON | • NC |
| Tirage sous-costal | • OUI | • NON | • NC |

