| Avez-vous reçu un vaccin Pneumocoque? | oui / non / ne sais pas |
| Si oui date de vaccination | |
| Avez-vous été vacciné contre rougeole, oreillons, rubéole? | oui / non / ne sais pas |
| Si oui date de vaccination | |

Co-infections

| |
|--|
| Avez-vous une maladie inflammatoire chronique comme le syndrome du côlon irritable? |
| Vous a-t-on diagnostiqué une infection virale (autre que Covid-19) comme la grippe saisonnière depuis mars 2020? |
| Si oui, savez-vous quelle était la cause de l'infection? |
| Si oui, était-ce une infection respiratoire? |
| Si oui, quels médicaments vous ont été prescrits? |
| Si oui, avez-vous été hospitalisé pour cette infection? |
| Vous a-t-on diagnostiqué une infection bactérienne depuis mars 2020? |
| Si oui, savez-vous quelle était la cause de l'infection? |
| Si oui, était-ce une infection respiratoire? |
| Si oui vous a-t-on prescrit des antibiotiques? Si oui lesquels? |
| Si oui, quels autres médicaments vous a-t-on prescrits? |
| Si oui, avez-vous été hospitalisé pour cette infection? |
| Souffrez-vous d'infections persistantes? |
| Si oui, savez-vous quels micro-organismes causent cette infection? |
| Si oui, quels médicaments vous a-t-on prescrits? |

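### The CRF gives irritable bowel syndrome as the only example of chronic inflammatory disease in two items, without asking for the diagnosis, so this one comorbidity may be misclassified

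*Protocol*

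**What the plan says.** Annex 3 (the Predi-COVID CRF) asks about chronic inflammatory disease in two places.

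- After the comorbidity table, beside hypertension and COPD: "Maladie inflammatoire chronique (ex: syndrome du côlon irritable".
- In the Co-infections module, as a question to the participant: "Avez-vous une maladie inflammatoire chronique comme le syndrome du côlon irritable".

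The introduction to Annex 3 says who supplies the answers. For the ISARIC parts: "Les parties ISARIC peuvent être remplies à l'aide d'information du dossier médical ou à l'aide du patient". For the added modules: "Les modules complémentaires sont à renseigner avec le patient". Section 10 adds that a trained nurse or research associate completes the form, that home patients are interviewed by phone, and that source data for a hospital stay are available from the hospitals or the national e-health database.

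On use of the data, section 3.1 sets out to "identify clinical, epidemiological and omics characteristics associated with the severity of COVID-19". Section 11.4 states: "A logistic model will be used to study whether the risks of hospitalisation, intensive care admission or intubation" depend on a given factor. Mortality is a further outcome there, and the models adjust for age, gender and possible confounders.

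**The concern.** Irritable bowel syndrome is by definition a functional bowel disorder, so it is a wrong example of a chronic inflammatory disease. The wording suggests a confusion with inflammatory bowel disease, although the protocol does not say so. Because it is the sole example, a participant with irritable bowel syndrome, or the staff member filling in the form, is led towards 'yes'. Someone with a true chronic inflammatory disease gets no correct prompt and may answer 'no'.

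The form has little to correct this. Neither item asks which disease is meant, whereas the infection questions in the same module do have follow-up questions. Rheumatological disease has its own line in the comorbidity table, but inflammatory bowel disease has none. The consistency checks in section 10 would not detect the problem, because two items sharing the same wrong example would tend to agree.

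At stake is one candidate risk factor for severity. It is also a plausible covariate for the cytokine and immune-phenotype endpoints in section 4.2 and the stool microbiome work in section 7.2, though the protocol does not assign it that role. An analysis plan cannot repair the item from the CRF field alone.

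**Working it through.** The plan states no figure for this item, so there is nothing to reproduce. The check asks how far an association could be distorted.

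**Inputs.** The reference risk ratio of 2 is borrowed from section 11.2 ("would allow to find a risk ratio of severe disease above 2 for the selected risk factor with a power of 80"%). Everything else is assumed, because the documents give no values:
- a, prevalence of true chronic inflammatory disease: 1–5%
- b, prevalence of irritable bowel syndrome without it: 0.5–10%
- s, share of b who answer 'yes': 25–100%

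**Error unrelated to severity.** Suppose all true cases answer 'yes' and people with irritable bowel syndrome only have risk ratio 1. Then:

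f = a / (a + b × s), the true share of 'yes' answers

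observed RR = 1 + f × (2 − 1)

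| a | b | s | f | observed RR |
|---|---|---|---|---|
| 1% | 10% | 100% | 0.01/0.11 = 0.09 | 1.09 |
| 2% | 5% | 50% | 0.02/0.045 = 0.44 | 1.44 |
| 5% | 5% | 50% | 0.05/0.075 = 0.67 | 1.67 |
| 5% | 0.5% | 25% | 0.05/0.05125 = 0.98 | 1.98 |

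With a correct example and no false 'yes' answers, f = 1 and the risk ratio stays at 2. False answers form the majority only when b × s exceeds a. True cases who answer 'no' would lower f further and slightly raise the risk in the 'no' group, so they too pull towards 1.

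**Error differing by hospitalisation.** Take 100,000 people with a = 2% and b = 5%. Assume a hospitalisation risk of 7% without and 14% with true disease. The 7% is only a convenient round figure, also used in section 11.2 ("when the prevalence of the disease is above 7"%). The groups are then:
- true disease: 2,000 (280 hospitalised, 1,720 at home)
- irritable bowel syndrome only: 5,000 (350 and 4,650)
- neither: 93,000 (6,510 and 86,490)

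If 25% of hospitalised but 100% of home participants with irritable bowel syndrome answer 'yes':
- 'yes' group: (280 + 87.5) / (367.5 + 1,720 + 4,650) = 367.5/6,737.5 = 5.45%
- 'no' group: (6,510 + 262.5) / (6,772.5 + 86,490) = 6,772.5/93,262.5 = 7.26%
- observed RR = 0.75

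With the two shares reversed:
- 'yes' group: (280 + 350) / (630 + 1,720 + 1,162.5) = 630/3,512.5 = 17.94%
- 'no' group: 6,510 / (6,510 + 86,490 + 3,487.5) = 6,510/96,487.5 = 6.75%
- observed RR = 2.66

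These two cases are deliberately extreme. They show that the direction is not guaranteed, and they do not predict the size.

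**The case against.** The strongest reply is that this is one badly worded yes/no item among about twenty comorbidities. No section names it as a selected risk factor or covariate, section 2.3 does not list it among the known risk factors, and nothing says that it feeds the Charlson index. Trained staff complete the form, so participants do not meet the wording unaided. The comorbidity table also has a free-text line for other notable risk factors, where a diagnosis could be written.

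Most of this stands, and it limits the importance of the point. It does not remove the error. The Co-infections question is put to the participant as worded, and in the comorbidity list the wrong example guides the staff. The free-text line may catch some true cases but does not identify false 'yes' answers.

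A reader might go further and infer that most 'yes' answers will be false. That needs prevalences and answering behaviour that the documents do not give, and it fails over part of the assumed range (f from 0.09 to 0.98). Nor do the documents support the inference that the error is irrecoverable. Section 10 gives access to hospital source data, and follow-up contacts run to 24 months (section 7.1).

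**Conclusion.** The point holds as a data-collection error limited to one comorbidity variable. Both CRF items use a wrong and sole example and record no diagnosis, so false-positive answers, and possibly missed true cases, are to be expected. How many cannot be known from the documents.

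If the error is unrelated to severity, the association is pulled towards 1. On the assumed inputs, a true risk ratio of 2 would appear as about 1.1 to 1.98. A reader might conclude that any association with severity will be diluted, but the protocol does not support that. Hospital data may come from source records and home data come from telephone interview, and hospitalisation is itself a main evaluation criterion (section 4.1). The error may therefore depend on the outcome, and the bias could go either way. All risk ratios here are illustrative. The correction is worth making because the wording is plainly wrong and cheap to change, not because a large bias has been shown.

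**What to change.** 1. In both Annex 3 items, remove irritable bowel syndrome as the example. Use correct examples, such as chronic inflammatory bowel disease (Crohn's disease, ulcerative colitis), and state that they are not exhaustive so that the category is not narrowed to bowel disease.
2. Add a free-text diagnosis to each item. If irritable bowel syndrome is of interest, record it as a separate yes/no item.
3. Check existing 'yes' answers against the medical record or at the next contact, applying the same rule to hospital and home participants as far as possible so that the check does not itself depend on severity. Until then, do not analyse the item as inflammatory disease.
4. Record which CRF version each answer came from. Checking only the 'yes' answers will not find true cases recorded as 'no', and any report should say so.

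For adults, the check must be done while records can still be linked: section 14 has the correspondence table deleted five years after the end of the study. Only the French CRF is annexed, so any other language version should be checked for the same wording.

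The cost is a small CRF revision and a check of existing 'yes' answers.

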| Objectives | The study aims at identifying factors associated with the COVID-19 disease severity. COVID-19 patients with severity criteria will be compared to patients with mild disease managed at home. |

| | |
|----------------------------|---|
| | A deep phenotyping related to the symptoms of the disease as well as biosampling allowing for laboratory-based and computational analytics will be performed. |
| Evaluation criteria | Severity of symptoms will be evaluated by the occurrence of an hospitalisation, the duration of the hospitalisation, the occurrence of ICU (or equivalent structures) stay, the duration of ICU, the need for supplemental oxygen, the need for ventilation and the duration of both, the need for a transfer to another hospital, the impact of infection on daily activities. As knowledge on covid is evolving very quickly, additional criteria may have to be added. |
| Study design | Predi-COVID is a prospective cohort study composed of adults and children positively tested for COVID-19 in Luxembourg, followed digitally for monitoring participants' health evolution and symptoms at home. Participants will be actively followed for 14 days from the time of confirmation of diagnosis, whether they are at the hospital or at home in isolation or quarantine. Short evaluations will be also performed at week 3 and week 4 and then monthly for a period up to 12 months to assess potential long term consequences of COVID-19. The last monthly questionnaire will be more detailed to provide a specific focus on long-COVID symptoms evaluation and will be completed at M12, M15 and M24.. All participants will be followed digitally and a subsample will participate in a sample collection. |

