4. EVALUATION CRITERIA

4.1 Main Evaluation Criteria

- **Hospitalization** : Hospitalisation and Duration of hospitalization (days)
- **Intensive care** : intensive care / resuscitation and duration of intensive care / resuscitation
- **Ventilation** : ventilation and duration of ventilation
- **Transfert to a hospital outside Luxembourg**
- **Clinical severity**
- **Death**

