| __/__/20__ | 
 • Ecouvillon nasal  Ecouvillon oropharyngé • Combinaison écouvillon nasal/oropharyngé • Crachats  LBA  Aspiration endotrachéale • Urine  Ecouvillonnage rectal  Sang • Autre, spécifier : __ | 
 • PCR • Culture • Autre, préciser : | 
 • Positif • Négatif • N/A | | |

| | | | | | |
|------------|---|--|---|--|--|
| __/__/20__ | 
 ● Ecouvillon nasal  Ecouvillon oropharyngé ● Combinaison écouvillon nasal/oropharyngé ● Crachats  LBA  Aspiration endotrachéale ● Urine  Ecouvillonnage rectal  Sang ● Autre, spécifier : __ | 
 ● PCR ● Culture ● Autre, préciser : | 
 ● Positif ● Négatif ● N/A | | |
| __/__/20__ | 
 ● Ecouvillon nasal  Ecouvillon oropharyngé ● Combinaison écouvillon nasal/oropharyngé ● Crachats  LBA  Aspiration endotrachéale ● Urine  Ecouvillonnage rectal  Sang ● Autre, spécifier : __ | 
 ● PCR ● Culture ● Autre, préciser : | 
 ● Positif ● Négatif ● N/A | | |

SECTION QUOTIDIENNE (compléter un exemplaire à l'admission à l'hôpital, un à l'admission en Unité de Soins Intensifs, et quotidiennement jusqu'au 14^e jour ou sortie du patient ou décès)

| SECTION QUOTIDIENNE |
|---|
| 
DATE de l'examen (JJ/MM/AAAA): [][][][]/[][][]/[][][][][][][][][]
 
Renseigner la valeur la plus mauvaise observée entre 00h00 à 24:h00 le jour de l'examen (si non disponible marquer 'N/A') :
 |

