| Si OUI, préciser  Légère  Modérée  Sévère • NC | | | | Anémie | • O U I | • N O N | • N / A |
| Pneumothorax | • O U I | • N O N | • N / A | Rhabdomyolyse | • O U I | • N O N | • N / A |
| Epanchement pleural | • O U I | • N O N | • N / A | Maladie rénale aiguë/Insuffisance rénale aiguë | • O U I | • N O N | • N / A |
| Pneumonie organisée cryptogénique (POC) | • O U I | • N O N | • N / A | Hémorragie digestive | • O U I | • N O N | • N / A |
| Bronchiolite | • O U I | • N O N | • N / A | Pancréatite | • O U I | • N O N | • N / A |

| | | | | | | | |
|--|---------------|---------------|---------------|-----------------------|---------------|---------------|---------------|
| Méningite/Encéphalite | • O U I | • N O N | • N / A | Dysfonction hépatique | • O U I | • N O N | • N / A |
| Crise d'épilepsie | • O U I | • N O N | • N / A | Hyperglycémie | • O U I | • N O N | • N / A |
| AVC | • O U I | • N O N | • N / A | Hypoglycémie | • O U I | • N O N | • N / A |
| Insuffisance cardiaque congestive | • O U I | • N O N | • N / A | Autre | • O U I | • N O N | • N / A |
| Endocardites /Myocardite /Péricardite | • O U I | • N O N | • N / A | Si OUI, préciser : __ | | | |
| Arythmie cardiaque | • O U I | • N O N | • N / A | | | | |
| Ischémie cardiaque | • O U I | • N O N | • N / A | | | | |

SECTION PRINCIPALE

| |
|--|
| TRAITEMENT : Le patient a-t-il reçu/nécessité pendant son hospitalisation ? |
|--|

Admission en unité de soins intensifs ou unité de réanimation ?

OUI NON N/A Si OUI, durée totale du séjour : __jour(s)

Si OUI, date d'admission :

[_] []/[_] []/[2_] [0_] [] [] N/A date de

sortie : [] []/[] []/[2_] [0_] [] [] N/A

Oxygénothérapie ? OUI NON N/A

Ventilation non-invasive ? (par exemple **VSPPC**, **VSPPBI**) OUI NON N/A

Ventilation mécanique ? OUI NON N/A Si OUI, durée totale : __jours

Ventilation en décubitus ventrale ? OUI

NON N/A **Inhalation de Monoxyde**

d'Azote ? OUI NON N/A

Trachéotomie OUI NON N/A

ECMO ? OUI NON N/A

Epuration/hemofiltration rénale /dialyse ? OUI NON N/A

Inotropes/vasopresseurs ? OUI NON N/A

: date première fois/début :

[_] []/[] []/[2_] [0_] [] [] N/A date dernière

fois/fin : [] []/[] []/[2_] [0_] [] [] N/A

Autre intervention ou procédure (préciser) : __

TRAITEMENTS REÇUS PENDANT L'HOSPITALISATION OU A LA SORTIE :

Antiviral ? OUI NON N/A Si OUI : Ribavirine Lopinavir/Ritonavir Interféron alpha
 Interféron beta

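### Oxygen and non-invasive ventilation have no total-duration field on the CRF, and the daily form that could supply their durations has three conflicting end points

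*Protocol*

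**What the plan says.** **Endpoint text.** The evaluation criteria in the synopsis include "the need for supplemental oxygen, the need for ventilation and the duration of both". Section 4.1 lists "ventilation and duration of ventilation" among the main criteria and does not say whether ventilation means invasive, non-invasive or either. Section 11.4 plans descriptive statistics for "hospitalisation, intensive care / resuscitation admission, ventilation, their duration, death and severity of the disease", while its logistic model refers to intubation. Section 11.5 promises the durations in weekly interim tables.

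**CRF, end-of-stay treatment page (Annex 3).** Three respiratory supports appear in sequence:
- oxygen: "Oxygénothérapie ? OUI NON N/A", with nothing after it;
- non-invasive ventilation: "Ventilation non-invasive ? (par exemple", followed by examples and yes/no boxes only;
- mechanical ventilation: "Ventilation mécanique ? OUI NON N/A Si OUI, durée totale : __jours".

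ICU stay on the same page also has a total duration, but it is not a respiratory support.

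**CRF, daily section (Annex 3).** For each calendar day it asks yes/no about non-invasive ventilation, mechanical ventilation and high-flow nasal oxygen. It has a field for FiO2 or litres per minute, filled in if the measurement was done. The section heading says when to complete it: "compléter un exemplaire à l'admission à l'hôpital, un à l'admission en Unité de Soins Intensifs, et quotidiennement", and then names the 14th day, discharge or death as the end.

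**The concern.** A duration named as a severity criterion should have a dependable source on the form. Mechanical ventilation has two: the end-of-stay total and the daily record. Non-invasive ventilation has only the daily record. Conventional oxygen has neither a total nor a daily yes/no item.

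The daily record is complete only if the form is filled in for the whole stay, and the protocol contradicts itself on how long that is. If staff follow the shortest rule, days after the cut-off are never collected for the two supports without a total. Section 11.4 says missing endpoint data will not be replaced. An analysis plan can define how a duration is derived, but it cannot recover days that were not recorded. Truncation would fall on the longest courses, which matter most in a study of severity.

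**Working it through.** The protocol states no figure to reproduce. The check sets the fields side by side and then applies them to illustrative patients.

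**Step 1. Sources for each duration (Annex 3).**

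| Support | End-of-stay total | Daily yes/no item |
|---|---|---|
| Mechanical ventilation | Yes, in days | Yes |
| Non-invasive ventilation | No | Yes |
| High-flow nasal oxygen | No | Yes |
| Conventional oxygen | No | No; inferred from FiO2 or L/min if done |

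**Step 2. Length of the daily record.**

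| Place | End point |
|---|---|
| Section 5, Study design | Death or discharge |
| Annex 3, general structure of the CRF | Discharge or death |
| Section 7.1, schedule table | Up to 30 days |
| Annex 3, heading of the daily section | Day 14, discharge or death |

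These are three different rules. I read the last as whichever comes first, since otherwise day 14 would have no function.

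**Step 3. Illustrative patients.** These are assumptions, not trial data. Day 1 is admission, ventilation counts as either type, and no calendar day has both types.

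- (a) Non-invasive on days 1-5: true duration 5.
- (b) Non-invasive on days 1-6, then mechanical on days 7-26: 6 + 20 = 26.
- (c) Mechanical on days 1-20, then non-invasive on days 21-24: 20 + 4 = 24.

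The best derivation from the form as it stands is: duration = mechanical days from the end-of-stay total + non-invasive days counted on the daily forms.

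| Patient | True | Derived, day-14 rule | Derived, 30-day rule or discharge/death |
|---|---|---|---|
| (a) | 5 | 0 + 5 = 5 | 5 |
| (b) | 26 | 20 + 6 = 26 | 26 |
| (c) | 24 | 20 + 0 = 20 | 20 + 4 = 24 |

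Only (c) loses days, and only under the day-14 rule: 24 - 20 = 4, and 4/24 = 17%. Under the 30-day rule, a loss of the same kind would begin after day 30.

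**Step 4. Oxygen.** The same cut-off applies, with no total as backup. Up to the cut-off, a day on conventional oxygen has to be inferred from an FiO2 or flow entry, which exists only where the measurement was marked as done. No frequency for any of these patterns is given in the protocol, so a cohort-level loss cannot be estimated.

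**The case against.** The strongest objection is that nothing is missing. The daily form asks about non-invasive ventilation every calendar day, it sits in the same CRF as the end-of-stay page, and how the two combine is ordinary analysis-plan detail.

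Much of this stands. A reader who sees only the end-of-stay page might infer that the main endpoint leaves out non-invasive ventilation altogether. The documents do not support that: no section ties duration of ventilation to the end-of-stay field, and the daily form can supply the non-invasive days. A reader might also take day 14 as the settled end of daily collection and conclude that long courses are generally cut to 14 days. That is not supported either. The day-14 wording stands in one place against three others, and even under it mechanical days keep their total, so patients (a) and (b) are recovered in full.

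Oxygen should not be overstated. Its duration is named in the synopsis but not among the main criteria in 4.1 or the durations listed in 11.4. Section 10 also provides access to hospital source data, so the information is probably retrievable.

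What the objection does not answer is the contradiction about when daily recording stops. The form lets a non-invasive or oxygen day after day 14 go unrecorded while following its own heading.

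**Conclusion.** The point holds in limited form. Among respiratory supports, only mechanical ventilation has a total duration. The durations of non-invasive ventilation and oxygen depend on a daily form whose end point is stated in three incompatible ways, and conventional oxygen is not asked about directly even there. Section 4.1 does not say which ventilation types count.

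For patient (c), the loss runs from none (30-day rule, or discharge or death) to 4 of 24 days, 17% (day-14 rule). This assumes that the derivation uses both CRF sources, that daily forms are complete up to the cut-off, and that missing days are not retrieved from the hospital record. This is a cheap improvement to data collection; it does not show that the main endpoint is invalid.

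**What to change.** 1. On the end-of-stay treatment page in Annex 3, give oxygen therapy and non-invasive ventilation the same total-days field that mechanical ventilation already has.
2. Reconcile the end point of the daily form across section 5, the section 7.1 table, the general CRF instructions and the heading of the daily section, so that one rule appears in all four places.
3. State in section 4.1 which types of ventilation count towards its duration, and report mechanical days as a separate, named component.

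The cost is two CRF fields and a few sentences. For patients already enrolled, the two totals can be entered retrospectively from the hospital records to which section 10 gives access. That small entry task is the main downside.
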